## **10. Clinical Investigation Evaluations, Procedures and Assessments**

### **10.1. METHOD OF ASSIGNING SUBJECTS**

No specific methods (e.g. randomization, blinding, or stratification) for assigning subjects are used in this clinical investigation plan (CIP). Consecutive subjects at each site meeting all the eligibility criteria will be enrolled in this clinical investigation.

### **10.2. PROCEDURES**

Subjects in the clinical investigation will undergo placement of the ReUnion RFX System. Please see the approved Instructions for Use and Operative Technique Manuals for a detailed description of the medical device(s) and instrumentation, intended use information and associated risk. Any additional clinically indicated procedures are permitted as deemed necessary by the clinical investigation investigator.

### **10.3. FOLLOW-UP EVALUATIONS**

Subjects in this clinical investigation will be evaluated at Preoperative, Operative/Discharge, and at 6 Weeks (4 weeks – 8 weeks), 6 Months (24 weeks – 28 weeks), 12 Months (48 weeks- 56 weeks), 24 Months (100 – 108 weeks) and annually thereafter. The follow-up evaluations will include assessment of device-related AEs/incidents, radiographs and ASES Shoulder Score.

Investigative site personnel will contact subjects prior to their scheduled follow-up evaluations to encourage compliance with clinical investigation visits and participation.

If a subject misses a visit and is outside of the visit window, every effort should be made to collect data instead of noting the visit as missed.

#### 10.4. SCHEDULE OF EVENTS

Assessment	Pre-Operative	Operative/ Discharge	6 Weeks a, b (+/- 2 weeks)	6 Months a, b (+/- 3 weeks)	12 Months a, b (+/- 4 weeks)	24 Months a, b (+/- 4 weeks)	Annually b (+/- 4 weeks)
Informed Consent	X						
Demographics & Medical History	X						
Inclusion/Exclusion	X						
Physical Exam	X		X c	X c	X c	X c	X c
Surgical Procedure		X					
ASES Shoulder Score	X		X d	X d	X d	X d	X d
Image Evaluation e, f	X	X	X	X	X	X	X
Subject Disposition g			X	X	X	X	X
	Device-Related AEs/Incidents & Reoperations will be collected throughout the course of the clinical investigation.						
	
 
a. Follow-up visit schedule to reflect Institution's Standard of Care practices
 
b. If the subject misses a visit and is outside of the visit window, then every effort should be made to collect data instead of noting visit as missed. Visit windows are calculated from index event, and not from previous visit.
 
c. Evaluation may be collected when subject presents in-clinic for study visit.
 
d. Evaluation can be collected via phone.
 
e. Radiograph collection should follow Institution's Standard of Care practices and no additional x-rays should be made for study purposes.
 
f. CT scans may be collected if part of Institution's Standard of Care practices.
 
g. Subject Disposition assessment will occur at any time point for subject withdrawal prior to the completion of the clinical investigation.
 
						

Table 1: Schedule of Events

## 11. Statistical Methods

By clinical investigation arm, the 24 months postoperative results for subjects implanted with the ReUnion RFX System will be compared to a historical group and results reported by respective clinical outcome data in the scientific literature. The benchmark sources and values will serve as the control group for the ReUnion RFX System subjects. Hypotheses are developed for each of the two clinical investigation arms.

The Statistical Analysis Plan (SAP) lists all variables/questions within this clinical investigation. Therefore, no additional “evaluation” chapter is required nor needed for this CIP.

Data will be captured via IBM Clinical Development electronic data capture (EDC) system and statistical analysis will be performed using IBM SPSS. All statistical hypotheses tests will be with confidence levels ( $1-\alpha$ ) of 95% and power ( $1-\beta$ ) of 80%. The significance level ( $\alpha$ ) is 0.05 and the beta-value ( $\beta$ ) is set to 0.20. Therefore, p-values  $\leq 0.05$  will indicate statistical significance.

Results will be presented using summary tables and optionally supported by graphs. For detailed information per variable, see SAP.

The primary endpoint of the clinical investigation is to demonstrate non-inferiority of the device to the selected literature controls (benchmark), as measured by the ASES Shoulder Score at 24 Months post-operative.

[figure not shown]
## 11.1. DETERMINATION OF SAMPLE SIZE

The determination of sample size is based on benchmark sources and values.

### 11.1.1. Sample Size Justification - Arm A (TSA/HA)

Benchmark and Objectives for Clinical Investigation						
Endpoint	Non-inferiority (equal or better) of the ASES Shoulder Score in relation to the officially cleared indications in comparison to respective clinical outcome data in the scientific literature.					
	Meta-analysis by Shukla et. al., 2016 [1]					
Estimated drop-out rate	56% (confirmed by Medical Expert, see Cuff et al. [2])					
Benchmark Sources & Values ASES [points] for Arm A (TSA/HA)						
Values from Shukla et. al used that were given for Hemiarthroplasty						
Source		Mean	Std. Dev.			
No.	Title					
1	Sebastia-Forcada, 2014 [3]	N/A	N/A			
2	Baudi, 2014 [4]	51.3	25.4			
3	Chalmers, 2014 [5]	66.0	31.0			
4	Cuff, 2013 [6]	62.0	14.0			
5	Garrigues, 2012 [7]	47.4	12.75			
6	Young, 2010 [8]	67.0	18.5			
7	Gallinet, 2009 [9]	N/A	N/A			
Identified Cleared Indications (Arm A & B)						
No.	Indication					
1	Aseptic necrosis of the humeral head					
2	Painful, disabling joint disease of the shoulder resulting from degenerative arthritis, rheumatoid arthritis or post-traumatic arthritis					
3	Proximal humeral fractures and/or dislocation					
4	Clinical management problems where arthrodesis or alternative reconstructive techniques are less likely to achieve satisfactory results					
5	Revision of previous unsuccessful total shoulder replacement, resurfacing or other procedure					
Explorative Analysis - ASES (single group) - for Arm A (TSA/HA)						
Acceptance Criteria						
Confidence Interval (CI)		0.95 (95%) two-sided				
Software Used		IBM SPSS V20				

Descriptives						
Post-Op ASES Mean		Statistic	Std. Error			
Mean		58,7400	3,97185			
95% Confidence Interval for Mean	Lower Bound	47,7124				
	Upper Bound	69,7676				
Median		62,0000				
Std. Deviation		8,88133				
Minimum		47,40				
Maximum		67,00				
Interquartile Range		17,15				
Post-Op ASES Std.Dev.	Mean	20,3300	3,46719			
		Red line: Pooled mean ASES Blue lines: 95% CI of pooled mean ASES Black line: Pooled median pooled ASES Box: Interquartile Range Green Line: Pooled mean ASES minus std. dev. ASES $58.74 - 20.33 = 38.41$ points				
Acceptance Criteria for Sample Size Calculation						
Significance Level ( $\alpha$ )	0.05 (5%)					
Power (1- $\beta$ )	0.80 (80%)					
Confidence Interval (CI)	0.95 (95%)					
Tails	2					
Path	Non-inferiority – ReUnion RFX Arm A (TSA/HA) (A) $\geq$ Benchmark (B, explorative analysis in this document)					
Hypotheses Pair	Null ( $H_0$ )		A – B $< -\theta$			
	Alternative ( $H_1$ )		A – B $\geq -\theta$			
Benchmark Timepoint	24 months postoperative					
Benchmark no. of sources	5					
Benchmark Mean	58.74 (pooled mean ASES [points])					
Benchmark Std. Dev.	20.33 (pooled std. dev. ASES [points])					
Benchmark Value	Pooled mean ASES minus pooled std. dev. ASES					
Non-Inferiority Margin (- $\theta$ )	$58.74 - 20.33 = 38.41$ points					
Software Used	IBM SPSS Sample Power V3.0					
IBM SPSS Sample Power Output						
One goal of the proposed clinical investigation is to test the null hypothesis that the population mean is 58.74 points. The criterion for significance (alpha) has been set at 0.05. The test is 2-tailed, which means that effects in both directions will be interpreted. With the proposed sample size of 10 cases, the clinical investigation will have power of 80.3% to yield a statistically significant result. This computation assumes that the population from which the sample will be drawn has a mean of 58.74 points with a standard deviation of 20.33 points. The observed value will be tested against a theoretical value (constant, non-inferiority margin) of 38.41 points.						

[figure not shown]
Estimated overall drop-out rate is 56% which leads to the requirement of enrolling an additional 6 subjects into the clinical investigation.

Sample Size	Overall number of subjects to be enrolled: 16 subjects (rounded up to 20 subjects)
Overall Sample Size (multiplied by number of indications = 5)	100 subjects

Table 2a: Sample Size Justification Arm A (TSA/HA)

[figure not shown]

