Acceptance Criteria for Sample Size Calculation		
Significance Level (<math>\alpha</math>)	0.05 (5%)	
Power (1-<math>\beta</math>)	0.80 (80%)	
Confidence Interval (CI)	0.95 (95%)	
Tails	2	
Path	Non-inferiority – ReUnion RFX Arm B (RSA) (A) $\geq$ Benchmark (B, explorative analysis in this document)	
Hypotheses Pair	Null ( $H_0$ )	$A - B < -\theta$
	Alternative ( $H_1$ )	$A - B \geq -\theta$
Benchmark Timepoint	24 months postoperative	
Benchmark no. of sources	5	
Benchmark Mean	74.48 (pooled mean ASES [points])	
Benchmark Std. Dev.	11.08 (pooled std. dev. ASES [points])	
Benchmark Value Non-Inferiority Margin (-<math>\theta</math>)	Pooled mean ASES minus pooled std. dev. ASES $74.48 - 11.08 = 63.40$ points	
Software Used	IBM SPSS Sample Power V3.0	
IBM SPSS Sample Power Output		
One goal of the proposed clinical investigation is to test the null hypothesis that the population mean is 74.48 points. The criterion for significance (alpha) has been set at 0.05. The test is 2-tailed, which means that effects in both directions will be interpreted. With the proposed sample size of 10 cases, the clinical investigation will have power of 80.3% to yield a statistically significant result. This computation assumes		

that the population from which the sample will be drawn has a mean of 74.48 points with a standard deviation of 11.08 points. The observed value will be tested against a theoretical value (constant, non-inferiority margin) of 63.40 points.

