### 11.3.2. Primary Analysis / Endpoint

The objective of the clinical investigation is to demonstrate the non-inferiority (equal or better) of the ASES Shoulder Score in relationship to the officially cleared indications in comparison to respective clinical outcome data in the scientific literature.

Data collection of ASES Shoulder Score will be collected according to the schedule in Table 1, Schedule of Events. This will be repeated annually in all subjects who have the prosthesis with full or partial implant survival (including all subjects without removal of all endo-prosthesis components).

The 24 months postoperative results for subjects implanted with ReUnion RFX System will be compared to a historical group and results reported by respective clinical outcome data in the scientific literature.

[figure not shown]
Higher ASES Shoulder Score results are linked to better subject results and vice versa.

The clinical investigation endpoint is non-inferiority to the control, meaning the clinical investigation result should be equal or better than the control. In this clinical investigation, an equal or better ASES Shoulder Score result means equal or more ( $\geq$ ). As only results from samples will be captured, results are mostly estimates of the true population parameter. These

estimates vary by a certain area, where it is expected that the true population parameter falls within. Based on this, it is required to specify a lower limit for the acceptable difference or zone of indifference, denoted as  $-\theta$ .

Hypotheses are developed to allow for a comparison of the 24 months postoperative ASES Shoulder Score effectiveness/performance between the two underlying populations. The 24 months post-operative ASES Shoulder Score is the primary endpoint of this clinical investigation. Hypothesis tests will be one-sided with a significance level  $\alpha$  of 5%.

[figure not shown]
Table 3a: Arm A (TSA/HA)

Hypothesis	Equations	Interpretation
Null ( $H_0$ )	$A - B < -\theta$	Central tendency of A is inferior to the central tendency of B.
	ReUnion RFX System (TSA/HA) – Control (Benchmark) $< -\theta$	
Alternative ( $H_1$ )	$A - B \geq -\theta$	Central tendency of A is non-inferior to the central tendency of B.
	ReUnion RFX System (TSA/HA) – Control (Benchmark) $\geq -\theta$	
		
Possible Evidence (p)	Possible Decisions	Possible Conclusions – ASES score

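### The non-inferiority margin −θ is given the value of a score (38.41, 63.40) instead of a difference (−20.33, −11.08), and the sample-size text names the assumed true mean as the null

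*Protocol*

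**What the plan says.** Protocol 11.1.1, 11.1.2 and 11.3.2 and SAP 3.1.1 and 3.2 give the same hypothesis pair for each arm: H0 is A − B < −θ and H1 is A − B ≥ −θ, where A is the device result and B the literature benchmark. Protocol 11.3.2 explains the role of −θ: "it is required to specify a lower limit for the acceptable difference or zone of indifference". On that definition −θ is a difference in ASES points.

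The value given to −θ is 38.41 in Arm A and 63.40 in Arm B (Protocol 8.1, 8.2, 11.1.1, 11.1.2 and 11.3.2; SAP 3.1.1, 3.2.1 and 3.2.2). Protocol 8.1, 8.2 and 11.3.2 and SAP 3.1.1 show in brackets, in the same sentence, where the number comes from: the control mean minus θ, that is 58.74 − 20.33 and 74.48 − 11.08.

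The power paragraph for Arm A opens with "One goal of the proposed clinical investigation is to test the null hypothesis that the population mean is 58.74 points". It then takes 58.74 as the true mean and 20.33 as the SD, and ends with "The observed value will be tested against a theoretical value (constant, non-inferiority margin) of 38.41 points". The Arm B paragraph has the same form: "One goal of the proposed clinical investigation is to test the null hypothesis that the population mean is 74.48 points", followed by "The observed value will be tested against a theoretical value (constant, non-inferiority margin) of 63.40 points". Both state 80.3% power with 10 cases. SAP 3.2.1 and 3.2.2 repeat both paragraphs.

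The test itself is a one-sample t-test or sign test against 38.41 (Arm A) or 63.40 (Arm B). SAP Table 6.6.1 states it in that form without using θ.

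**The concern.** There is no concurrent control, so the fixed constant and its meaning are the whole primary criterion. One symbol stands for two quantities on different scales, and one sentence puts the null at the value assumed to be true.

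What is at stake is how the criterion is stated and reported. A report that copies the labelled margin would say that losses of 38.41 and 63.40 points were tolerated, when the planned test tolerates 20.33 and 11.08. A report that copies the named null would say that the benchmark mean itself was tested, when the test concerns a value one SD below it. The decision tables (Protocol Tables 3a and 4a; SAP Tables 3.1.1.1 and 3.1.1.2) reinforce this, because they read p ≤ 0.05 as the device being at least equal to the benchmark.

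**Working it through.** **Inputs** (Protocol 11.1.1 and 11.1.2; the same in SAP 3.2.1 and 3.2.2)

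- Benchmark mean, also the assumed true mean: 58.74 (A), 74.48 (B)
- SD: 20.33 (A), 11.08 (B)
- Constant tested against: 38.41 (A), 63.40 (B)
- n = 10; stated power 80.3%
- "The criterion for significance (alpha) has been set at 0.05", and "The test is 2-tailed, which means that effects in both directions will be interpreted"

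**Step 1. Reproduce the stated power.** For a one-sample t-test the noncentrality is √n × (true mean − null value) / SD, with n − 1 = 9 degrees of freedom.

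- Arm A: √10 × (58.74 − 38.41) / 20.33 = √10 × 1 = 3.16
- Arm B: √10 × (74.48 − 63.40) / 11.08 = √10 × 1 = 3.16

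The exact two-sided 5% power from the noncentral t distribution is 0.8031 in each arm, which matches 80.3%. The null values behind the plan's figure are therefore 38.41 and 63.40.

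**Step 2. Try the null named in the text.** With the null at 58.74 (74.48) and the true mean also 58.74 (74.48), the noncentrality is 0 and the power equals α, 5%. The sentence naming the benchmark mean as the null cannot describe the calculation that was run.

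**Step 3. Put each reading of −θ into A − B ≥ −θ**, that is, mean ≥ benchmark − θ.

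| Reading | Arm A threshold | Arm B threshold |
|---|---|---|
| −θ = 38.41 / 63.40, as printed | 58.74 + 38.41 = 97.15 | 74.48 + 63.40 = 137.88 |
| θ = 38.41 / 63.40, sign changed | 58.74 − 38.41 = 20.33 | 74.48 − 63.40 = 11.08 |
| θ = 20.33 / 11.08, from the bracket | 58.74 − 20.33 = 38.41 | 74.48 − 11.08 = 63.40 |

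Only the third row gives the planned test value, and only that row agrees with Step 1. The documents do not state the maximum ASES score. If it is 100 (an assumption), the literal Arm B threshold of 137.88 cannot be reached.

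**Step 4. Size of the mislabelling.** Labelled margin over the loss actually tolerated: 38.41 / 20.33 = 1.9 in Arm A and 63.40 / 11.08 = 5.7 in Arm B.

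**The case against.** The strongest reply is that nobody carrying out this plan would run the wrong test. The constants 38.41 and 63.40 are the same wherever the test is described, and SAP Table 6.6.1, which the analyst will follow, does not mention θ. The bracket beside the mislabelled value gives the key: 58.74 − 20.33 shows that θ is 20.33, and A − B ≥ −20.33 is the planned test. The power paragraph misnames its null in one sentence but then gives the correct true mean, SD and tested constant. The thresholds of 97.15 and 137.88 arise only if the bracket is ignored.

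All of that stands, and it limits the point. A reader might infer that the planned test is undefined, or that the power text sets a pass mark of 58.74 and 74.48. The documents support neither: the test can be recovered without ambiguity, and the power paragraph itself tests against 38.41 and 63.40.

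The reply does not remove the error. Neither document states outright that θ is 20.33 or 11.08, so the tolerated loss is never shown under its own name. The sentence explaining the test is also not free of slips: Protocol 11.3.2, in the Arm A text, attaches the RSA label to the test against 38.41, and the Arm B text of the same section then tests RSA against 63.40.

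**Conclusion.** The non-inferiority margin and the null hypothesis are misstated in both arms and both documents. The tolerated loss is 20.33 points in Arm A and 11.08 in Arm B, while the quantity labelled as the margin is 38.41 and 63.40. The null value is 38.41 and 63.40, while the power text names 58.74 and 74.48.

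This is a fault in the consistency of the decision rule. The subtractions are correct and the stated power reproduces. Sample size, power, test constants and test result do not change, and a reader should not conclude that any of them is wrong. The conclusion rests only on figures in the documents; the one outside assumption, a maximum score of 100, bears solely on whether 137.88 could be reached. Whether one SD is a defensible margin is a separate question, not settled here.

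Because this is the primary criterion of a study with no concurrent control, the correction should be made before the primary analysis is reported.

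**What to change.** In Protocol 8.1, 8.2, 11.1.1, 11.1.2 and 11.3.2, and SAP 3.1.1, 3.2.1 and 3.2.2, wherever the item occurs:

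- State θ = 20.33 (Arm A) and 11.08 (Arm B), so −θ = −20.33 and −11.08.
- Call 38.41 and 63.40 the test value, defined as benchmark mean minus θ, and stop calling them the margin.
- State H0: mean ≤ 38.41 (63.40) against H1: mean > 38.41 (63.40). Note that equality moves from H1 to H0.
- In the power text, name 38.41 and 63.40 as the null values and 58.74 and 74.48 as the assumed true means.

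In the same edit:

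- Reconcile the two-tailed sizing with the analysis text, which says "Hypothesis tests will be one-sided with a significance level" of 5%. At n = 10, two-sided 5% gives 80.3% power and one-sided 5% gives 89.8%.
- Correct the RSA label on the Arm A test in Protocol 11.3.2.
- Reword the decision tables in both documents so that p ≤ 0.05 reads as a mean above the benchmark minus θ.

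The cost is wording in two documents. No data, sample size or analysis changes.

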#### 11.1.2. Sample Size Justification - Arm B (RSA)

Benchmark and Objectives for Clinical Investigation					
Endpoint	Non-inferiority (equal or better) of the ASES Shoulder Score in relation to the officially cleared indications in comparison to respective clinical outcome data in the scientific literature.				
Meta-analysis by Shukla et al., 2016 [1]					
Benchmark Sources & Values ASES [points] for Arm B (RSA)					
Source	No.	Mean	Std. Dev.		
Source	Title	Mean	Std. Dev.		
1	Sebastia-Forcada, 2014 [3]	N/A	N/A		
2	Baudi, 2014 [4]	69.3	25.4		
3	Chalmers, 2014 [5]	80.0	11.0		
4	Cuff, 2013 [6]	77.0	3.75		
5	Garrigues, 2012 [7]	81.1	3.25		
6	Young, 2010 [8]	65.0	12.0		
7	Gallinet, 2009 [9]	N/A	N/A		
Identified Cleared Indications (Arm A & B)					
No.	Indication				
1	Aseptic necrosis of the humeral head				
2	Painful, disabling joint disease of the shoulder resulting from: degenerative arthritis, rheumatoid arthritis, or post-traumatic arthritis				
3	Proximal humeral fractures and/or dislocation				
4	Clinical management problems where arthrodesis or alternative reconstructive techniques are less likely to achieve satisfactory results				
5	Revision of previous unsuccessful total shoulder replacement, resurfacing or other procedure				
Explorative Analysis - ASES (single group) - for Arm B (RSA)					
Acceptance Criteria					

Confidence Interval (CI)	0.95 (95%) two-sided	
Software Used	IBM SPSS V20	
Descriptives		
Post-Op ASES Mean	Mean	74,4800 3,14124
	95% Confidence Interval for Mean	Lower Bound 65,7585 Upper Bound 83,2015
	Median	77,0000
	Std. Deviation	7,02403
	Minimum	65,00
	Maximum	81,10
	Interquartile Range	13,40
Post-Op ASES Std.Dev.	Mean	11,0800 4,00595
 
A box plot showing the distribution of Post-Op ASES Mean. The y-axis ranges from 60 to 85. The box represents the Interquartile Range (IQR) from approximately 68 to 78. The median is at 75. The whiskers extend from 65 to 81. A red horizontal line at 74.48 represents the Pooled mean ASES. Two blue horizontal lines at approximately 65.7585 and 83.2015 represent the 95% CI of the pooled mean ASES. A green horizontal line at 74.48 - 11.08 = 63.40 represents the Pooled mean ASES minus pooled std. dev. ASES.
		Red line: Pooled mean ASES Blue lines: 95% CI of pooled mean ASES Black line: Pooled median pooled ASES Box: Interquartile Range Green Line: Pooled mean ASES minus pooled std. dev. ASES $74.48 - 11.08 = 63.40$ points
Acceptance Criteria for Sample Size Calculation		
Significance Level (<math>\alpha</math>)	0.05 (5%)	
Power (1-<math>\beta</math>)	0.80 (80%)	
Confidence Interval (CI)	0.95 (95%)	
Tails	2	
Path	Non-inferiority – ReUnion RFX Arm B (RSA) (A) $\geq$ Benchmark (B, explorative analysis in this document)	
Hypotheses Pair	Null ( $H_0$ )	$A - B < -\theta$
	Alternative ( $H_1$ )	$A - B \geq -\theta$
Benchmark Timepoint	24 months postoperative	
Benchmark no. of sources	5	
Benchmark Mean	74.48 (pooled mean ASES [points])	
Benchmark Std. Dev.	11.08 (pooled std. dev. ASES [points])	
Benchmark Value Non-Inferiority Margin (-<math>\theta</math>)	Pooled mean ASES minus pooled std. dev. ASES $74.48 - 11.08 = 63.40$ points	
Software Used	IBM SPSS Sample Power V3.0	
IBM SPSS Sample Power Output		
One goal of the proposed clinical investigation is to test the null hypothesis that the population mean is 74.48 points. The criterion for significance (alpha) has been set at 0.05. The test is 2-tailed, which means that effects in both directions will be interpreted. With the proposed sample size of 10 cases, the clinical investigation will have power of 80.3% to yield a statistically significant result. This computation assumes		

that the population from which the sample will be drawn has a mean of 74.48 points with a standard deviation of 11.08 points. The observed value will be tested against a theoretical value (constant, non-inferiority margin) of 63.40 points.

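### The benchmark SDs labelled pooled (20.33 and 11.08) are plain averages of study SDs; with equal-weight pooling and fixed test values, two-sided power at n=10 is about 76% (Arm A) and 63% (Arm B), not 80.3%

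*Protocol*

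**What the plan says.** Protocol 11.1.1 and 11.1.2, repeated in SAP 3.2.1 and 3.2.2, list five study means and SDs per arm, without study sizes, and reduce them to one mean and one SD. The SDs are given as "20.33 (pooled std. dev. ASES [points" for Arm A and "11.08 (pooled std. dev. ASES [points" for Arm B. The Arm A mean is "58.74 (pooled mean ASES [points"; the Arm B mean is 74.48.

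The test value in each arm is the mean minus this SD: 38.41 in Arm A and 63.40 in Arm B. For Arm A the plan says: "The observed value will be tested against a theoretical value (constant, non-inferiority margin) of 38.41 points".

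Both arms carry the same power statement: "With the proposed sample size of 10 cases, the clinical investigation will have power of 80.3% to yield a statistically significant result". On the error rate: "The criterion for significance (alpha) has been set at 0.05". On sidedness: "The test is 2-tailed, which means that effects in both directions will be interpreted". Protocol 11.3.2 and SAP 3.1.1 describe the analysis differently: "Hypothesis tests will be one-sided with a significance level" of 5%.

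**The concern.** SDs are pooled through their variances. A plain average of unequal SDs is always smaller than the pooled SD at the same weights, and the gap widens as the SDs differ more. In Arm B they run from 3.25 to 25.4, so two very small values pull the average down.

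The SD enters the plan twice: it is the planning SD behind the only power statement, and it sets the distance from the benchmark mean to the test value. If it is too small, the stated power is too high for the test values that the plan fixes. A reader would also take the word pooled to mean that study variances and sizes had been used.

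**Working it through.** **Inputs** (protocol 11.1.1 and 11.1.2)

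- Arm A study SDs: 25.4, 31.0, 14.0, 12.75, 18.5. Assumed mean 58.74, test value 38.41, distance 20.33.
- Arm B study SDs: 25.4, 11.0, 3.75, 3.25, 12.0. Assumed mean 74.48, test value 63.40, distance 11.08.
- n = 10; alpha 0.05, two-sided in the sample size sections and one-sided in 11.3.2.

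**Step 1: what the labelled values are**

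- Arm A: (25.4 + 31.0 + 14.0 + 12.75 + 18.5)/5 = 101.65/5 = 20.33
- Arm B: (25.4 + 11.0 + 3.75 + 3.25 + 12.0)/5 = 55.4/5 = 11.08

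The standard errors printed beside them, 3.46719 and 4.00595, are exactly those of five unweighted data points. No weighting or variance pooling took place.

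**Step 2: the plan's own power**

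The power of a one-sample t-test comes from the noncentral t distribution with n − 1 degrees of freedom and noncentrality (distance/SD) × √n. The plan sets distance equal to SD, so the ratio is 1 in both arms. With n = 10 and two-sided 0.05, power is 0.8031. The stated 80.3% is reproduced.

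**Step 3: pooled SD at the plan's equal weights**

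Pooled SD = √(mean of SD²).

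- Arm A: (645.16 + 961 + 196 + 162.5625 + 342.25)/5 = 461.39; square root 21.48
- Arm B: (645.16 + 121 + 14.0625 + 10.5625 + 144)/5 = 186.96; square root 13.67

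The plan's values are lower by 1 − 20.33/21.48 = 5% and 1 − 11.08/13.67 = 19%.

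**Step 4: power with test values fixed at 38.41 and 63.40, n = 10**

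| | Distance/SD | Two-sided 0.05 | One-sided 0.05 | n for 80%, two-sided | n for 80%, one-sided |
|---|---|---|---|---|---|
| Plan, both arms | 1 | 80.3% | 89.8% | 10 | 8 |
| Arm A, SD 21.48 | 0.946 | 75.9% | 86.7% | 11 | 9 |
| Arm B, SD 13.67 | 0.810 | 62.7% | 76.4% | 14 | 11 |

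**Step 5: how far study sizes matter**

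Sizes are not in the documents, so these are assumptions.

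- One study three times as large as each of the others: Arm A SD 19.4 to 24.6, Arm B SD 11.7 to 17.8.
- Sizes drawn uniformly from 10 to 50 per study, central 95% of draws: Arm A SD 18.8 to 24.0, two-sided power 67% to 86%; Arm B SD 10.4 to 16.6, two-sided power 47% to 85%.

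**The case against.** Several points stand on the other side.

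- **The 80.3% is not a miscalculation.** It is exact for the stated inputs, and the plan says which SD it assumes. The fault is in that SD and its label.
- **76% and 63% are one scenario.** If the Arm A study with SD 12.75 is three times as large as each of the others, the Arm A SD is 19.39 and two-sided power is 83.8%. If the Arm B studies with SDs 3.75 and 3.25 are both three times as large, the Arm B SD is 10.46 and power is 84.6%.
- **The loss depends on holding the test values.** Under the plan's rule of mean minus SD, a larger SD widens the margin and power returns to 80.3%. But the pass marks would then fall to 58.74 − 21.48 = 37.26 and 74.48 − 13.67 = 60.81, so correcting an error would make non-inferiority easier to claim. Both documents state 38.41 and 63.40 as fixed constants, so holding them is the sounder reading.
- **Arm A clears 80% under the one-sided test.** Only Arm B then misses.

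A reader might infer that the trial is underpowered. The documents do not support that. Ten is a per-indication figure that the plan builds up to 100 subjects, while the test is run per arm, and the split between arms is not specified. If the split were even and 56% were lost (an assumption), 50 × 0.44 = 22 per arm would remain, and two-sided power with the equal-weight pooled SDs would be 98.8% and 95.2%.

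A reader might also count the unweighted benchmark means against the power. They do not affect it: the test value moves with the mean, so the distance is unchanged.

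**Conclusion.** The point holds as a correction to a label, an input and the figure derived from it. It is certain from the documents that 20.33 and 11.08 are averages of study SDs and not pooled SDs.

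The size of the effect is conditional on equal study sizes, test values held at 38.41 and 63.40, and n=10. On that basis two-sided power is about 76% in Arm A and 63% in Arm B. Under the one-sided 5% test it is about 87% and 76%. Arm B is therefore the arm that falls short of 80% on both readings.

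The actual shortfall, if any, cannot be fixed without the study sizes. The power of the per-arm test cannot be read from n=10 at all.

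**What to change.** In protocol 11.1.1 and 11.1.2 and SAP 3.2.1 and 3.2.2:

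1. Compute each pooled SD as the square root of the weighted mean variance, using study sizes from the cited meta-analysis. If these cannot be obtained, use 21.48 and 13.67 and say that they are equal-weight values.
2. Describe 20.33 and 11.08 as averages of study SDs wherever they are called pooled, including the objective and primary endpoint text.
3. Keep the test values at 38.41 and 63.40 as fixed constants, so that the larger SD does not lower the pass marks.
4. Restate the power at n=10, or the n for 80%, for the test actually planned, and give the same sidedness in the sample size and analysis sections. At equal weights the n for 80% is 11 and 14 two-sided, or 9 and 11 one-sided.

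The benchmark means need no change for this purpose; re-weighting them would move the test values that the restated power holds fixed. The cost is a desk recalculation and wording in two documents. The total of 100 can stay. The downside is that the stated power becomes less favourable, mainly in Arm B.
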